RESEARCH PROTOCOL

Version 1.5

Date 10/6/2016

Research Title: Objective, Prospective Measurement of Anterior Chamber Cell Grading Using Anterior Chamber Ocular Coherence Tomography

Short Title: Prospective OCT Measurement of AC Cells

Purpose:

- To determine the feasibility of objective measurement of anterior chamber (AC) cell count utilizing
 - the SPECTRALIS (Heidelberg Engineering, Franklin, MA) spectral domain optical coherence tomography (OCT) system
 - the iSCAN (Optovue, Fremont, CA) spectral domain OCT system
- To develop algorithms that automatically differentiate between cells and “noise” in the anterior chamber OCT (AC-OCT) images and objectively measure the cell density
- To correlate the objective AC cell density measurement and the subjective clinical AC cell grading
- To compare the objective AC cell density measurement with subject treatment outcomes

Introduction:

Treatment decisions for patients with uveitis are currently formulated largely on subjective clinical exam data with high interobserver variation.¹ The most used and most accurate of these subjective clinical data is anterior chamber (AC) cell grade, a measure of intraocular inflammation.¹ AC cell grade is measured by experienced clinicians who manually count the number of leukocytes in a 1mm by 1mm beam of light in the AC visible through a slit lamp stereoscope. The result is a “grade” for AC cells on a nonlinear, ordinal scale as follows: grade 0 is <1 cell, grade 0.5+ is 1-5 cells, grade 1+ is 6-15 cells, grade 2+ is 16-25 cells, grade 3+ is 26-50 cells, and grade 4+ is >50 cells.² The wide range of cells included in the higher grades means that a large change in anterior chamber inflammation might go unnoticed. For example, a patient with 28 cells at their last visit (grade 3+) but 48 cells at their current visit (still grade 3+) would have their 71% increase in intraocular inflammation go unnoticed, as they are still grade 3+. This has concerning implications for both the treatment of patients with intraocular inflammation and the evaluation of interventions that target intraocular inflammation (such as pharmaceuticals).

People with uveitis and people who recently underwent cataract extraction surgery often have intraocular inflammation on clinical exam. Those with uveitis are generally given anti-inflammatory medication to resolve their inflammation. Inflammation after cataract extraction surgery is generally self-resolving.

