Optical Coherence Tomography (OCT) uses infrared light with a central wavelength of 840 - 870 nm from a superluminescent diode to scan ocular structures and produce cross sectional and three dimensional images.^{3,4} It is considered a Class 1 laser product that, “does not pose any safety hazard whatsoever.”^{3,5}

RUTGERS APPROVED
THE STATE UNIVERSITY
OF NEW JERSEY

IRB ID: Pro20160000585
Approval Date: 10/24/2016
Expiration Date: 7/19/2017

Title: Prospective OCT Measurement of AC Cells

PI: [name]

OCT machines are used widely in ophthalmology clinics to image the retina and objectively measure glaucoma progression. It can also be used to image the anterior chamber.

A few studies have evaluated the feasibility of imaging the AC to objectively measure intraocular inflammation using optical coherence tomography (OCT). Many of these have used older, time domain OCT (TD-OCT) devices, with resolutions larger than most leukocytes.⁶⁻⁸ One has used newer, spectral domain OCT (SD-OCT) technology with promising results.⁹ No study that we are aware of, however, has either used the SPECTRALIS or iSCAN SD-OCT systems for these measurements, or correlated these measurements against clinical outcomes. We plan to use the SPECTRALIS and iSCAN SD-OCT systems to image the AC of subjects with intraocular inflammation, automate the objective reading of AC cell count from these images, correlate the objective count with the subjective clinical grade, and observe if the correlation is strong enough to guide treatment decisions.

Hypothesis:

Automated, objective measurement of anterior chamber cell count with the SPECTRALIS (Heidelberg Engineering, Franklin, MA) and iSCAN (Optovue, Fremont, CA) spectral domain optical coherence tomography systems cannot be used to guide the treatment of patients with intraocular inflammation.

Methods:

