Choice of which OCT system to use (SPECTRALIS or iSCAN) will depend on OCT and subject availability. Subjects will generally be asked to use the SPECTRALIS OCT system. If the SPECTRALIS is being used for clinic patients, subjects will be asked to instead use the iSCAN system. If they have time and agree, some subjects will be asked to use both systems to ensure similar results can be obtained from each system. The system used on a subject's first visit will determine which system they use for their entire enrollment. Subjects will use the same OCT system for the duration of their enrollment in this study.

Each enrolled subject will be scanned a total of between one and eight times over a period of two to eight weeks, depending on the dates of their scheduled follow up visits in clinic. The scans will only occur on their regularly scheduled clinic visits. The first scan will occur on the first visit where they are identified as eligible and they agree to participate. Patients with active intraocular inflammation in the uveitis clinic are generally prescribed anti-inflammatory medications and asked to return within a few days to weeks to evaluate resolution of the inflammation. Patients who recently underwent cataract extraction surgery are also asked to return within a few days to weeks to follow up the surgery. On these follow up visits, the subjects will be reminded that participation is optional and they will be asked to undergo another OCT scan. Subjects who agree will be scanned again on these follow up visits with the same procedure described above. This will allow us to identify both inflammation and resolution of inflammation on the study images and analyze the data as described in the last paragraph of this protocol. Non-patient control subjects will have the option of only undergoing one scan or individually scheduling follow-up visits for repeat scans for up to eight total scans over a period of two to eight weeks. No subject will be scanned more than eight times in total for this study.

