The scans performed by the SPECTRALIS and iSCAN OCT machines are non-contact procedures that use safe, infrared light. The subject rests their chin and forehead into plastic rests that are cleaned with alcohol between each use. The SPECTRALIS or iSCAN OCT can then image the subject's eye. The subject's eye will not be touched for this scan or for any part of this study. No eye drops will be used for this study, as none are required for these high quality, non-contact scans.

Title: Prospective OCT Measurement of AC Cells

PI: [name]

All study activities will be performed in the Doctor's Office Center suite 6100. Subject recruitment and the consent process will occur in exam rooms owned by Rutgers University in DOC 6100. Subjects who enroll in the study, as described above, will be brought to either DOC 6136 or DOC 6100A, where the SPECTRALIS OCT or iSCAN OCT, respectively, are stored and where the study scans will be performed; this room and the equipment are owned by Rutgers University. Data storage and analysis will take place on computers and in locked areas of DOC 6100 owned by Rutgers University.

A list of participating subjects with unique identification keys will be kept in the locked room of a secondarily locked research area by the study coordinator.

Data taken from the medical record will include: name, date of birth, medical record number, inflammation status, and ocular history. The name, date of birth, and medical record number will be used to coordinate scans for subject's follow-up visits. The inflammation status and ocular history will be used to make appropriate comparisons for the study.

Scan data will be stored in the SPECTRALIS or iSCAN OCT systems as is standard for clinical practice. Scan data will be taken from the OCT system via encrypted USB drive upon each subject's completion in the study. The data will then be de-identified, labeled with the unique identification key described above, and stored in the locked room of a secondarily locked research area. The key will remain on paper in a locked room in a secondarily locked research area in the DOC. Only the study coordinator and principle investigator will have access to the data.

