Subject risks include potential breach of confidentiality of information collected and the loss of 10-20 minutes of time required to complete the OCT scan process. The risk of breach of confidentiality of information is minimal due to the lack of collection of sensitive information and will be further minimized by storing data in locked and password protected files, as described above. Subject benefits include potentially increased understanding of intraocular inflammation and the new management standards that may be applied to their, and others', uveitis treatment in the future.

All subject data obtained will be confidential. Data will only be released in aggregate and no subjects' personal identifiers will be revealed.

De-identified image data from the SPECTRALIS and iSCAN OCT systems will be analyzed two ways. The first analysis methodology will be the manual identification of leukocytes on the OCT image by the staff uveitis specialists. The second analysis methodology will be the automatic identification of leukocytes on the OCT image by computer algorithm. The AC cell count results of the two analysis methodologies will be compared to subject's clinical AC cell grading. Statistical analysis using T-test and other statistical tools will be used to compare the study and the clinical AC cell count methodologies. Study AC cell count results will also be correlated with the actual subject treatment plans and outcomes to test the null hypothesis that the study results would not have been able to correctly guide subject treatment decisions.

References:

Title: Prospective OCT Measurement of AC Cells

PI: [name]

3. *User Manual: SPECTRALIS HRA+OCT.* Heidelberg Engineering GmbH;2012.
4. ISCAN. *Optovue* 2016; <http://www.optovue.com/products/iscan/>, 2016.
5. Laser Safety Information. *Laser Institute of America* 2016; https://www.lia.org/subscriptions/safety_bulletin/laser_safety_information. Accessed March 31, 2016.

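### The only named test, a T-test, does not measure the strength of correlation that the study aims at; no correlation estimate, clustered interval or limit for strong enough is set

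*Combined protocol and SAP*

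**What the plan says.** The Purpose section lists as an aim: "To correlate the objective AC cell density measurement and the subjective clinical AC cell grading". The Introduction turns this into a judgement. The investigators will "correlate the objective count with the subjective clinical grade, and observe if the correlation is strong enough to guide treatment decisions".

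The Introduction also describes the clinical measure. Clinicians "manually count the number of leukocytes in a 1mm by 1mm beam of light", and the result is reported as a grade "for AC cells on a nonlinear, ordinal scale as follows", with six levels from 0 to 4+.

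The analysis text is the last paragraph of Methods. It defines two readings of each OCT image, one manual and one automated, and says that "The AC cell count results of the two analysis methodologies will be compared to" the clinical grading. The method is then: "Statistical analysis using T-test and other statistical tools will be used to compare the study and the clinical AC cell count methodologies". A further sentence promises to correlate the OCT counts with the treatment given and its outcomes, as the test of the null hypothesis, again without naming a method.

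On repeat measurement, Methods says: "Each enrolled subject will be scanned a total of between one and eight times over a period of two to eight weeks". On extracted data it says: "Data taken from the medical record will include: name, date of birth, medical record number, inflammation status, and ocular history".

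No section names a correlation coefficient, a model, a confidence interval, a significance level or a value for strong enough.

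**The concern.** A T-test compares means, whereas the aim concerns strength of association with an ordinal grade. The form of the T-test is not stated, and it has three plausible readings:

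- (a) paired, OCT count against grade: the scales differ, so the result reflects units;
- (b) paired, OCT count against slit-lamp count: a legitimate test of mean bias, but not of correlation;
- (c) OCT count compared between groups of grades: this detects association, but merges grades and shows strength only indirectly.

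Two consequences follow. First, without a named estimate, interval and limit, whether the correlation is strong enough can be settled after the data are seen. Second, if a correlation is added later and each scan is treated as a separate subject, the evidence will be overstated.

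**Working it through.** The plan gives no figure to reproduce: the ceiling of 300 subjects comes with no power, precision or target correlation. The figures below illustrate the point on assumed inputs. From the documents come the grade cut-offs (Introduction) and the one to eight scans (Methods). Assumed are lognormal counts with median 8 and log-SD 1, rounded down; a latent correlation ρ between slit-lamp and OCT counts; a two-sided 5% level; and N = 100 with one scan each unless stated.

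**Paired T-test, readings (a) and (b).** Simulated rejection rates (4,000 runs per cell):

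| ρ | count vs grade | count vs count, equal scale | count vs count, OCT 20% low |
|---|---|---|---|
| 0 | 100% | 4% | 23% |
| 0.3 | 100% | 4% | 29% |
| 0.5 | 100% | 4% | 36% |
| 0.7 | 100% | 4% | 53% |
| 0.9 | 100% | 4% | 89% |

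An independent rerun agreed: at least 99.9% in the first column, 4-5% in the second, and 22% rising to 90% in the last.

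The last column can be checked by hand. The mean count is 8·e^0.5 = 13.19, so a 20% shortfall is a mean difference of 2.64. The count SD is √(64·e·(e−1)) = 17.29, and the OCT SD is 0.8 × 17.29 = 13.83. The correlation of the counts is (e^ρ − 1)/(e − 1), which is 0 at ρ = 0 and 0.849 at ρ = 0.9.

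- ρ = 0: SD of the difference = √(17.29² + 13.83²) = 22.14; t ≈ 10 × 2.64/22.14 = 1.19; power about 22%.
- ρ = 0.9: SD = √(17.29² + 13.83² − 2 × 0.849 × 17.29 × 13.83) = 9.16; t ≈ 2.88; power about 82% (the normal approximation is somewhat low for skewed data).

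With a fixed bias, then, the better the OCT count follows the clinical count, the more often the paired test calls the two different.

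**T-test between grade groups, reading (c).** With grades up to 1+ against 2+ and above, on log(1 + count), the standardised difference is 0.00, 0.54, 0.92, 1.43 and 2.12 at ρ = 0, 0.3, 0.5, 0.7 and 0.9. It does grow with the correlation. At ρ = 0.3 its power is 61%, against 79% for the Spearman test.

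**Why a limit is needed.** With one observation each at N = 300, the smallest significant r is t/√(N − 2 + t²) = 1.968/√(298 + 3.87) = 0.113. Significance therefore cannot stand in for strong enough. An estimate with an interval can be judged: with Fisher z and variance (1 + r²/2)/(N − 3) at N = 100, Spearman values of 0.45, 0.64 and 0.84 have 95% intervals of 0.27-0.60, 0.49-0.75 and 0.76-0.90.

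**Repeat scans.** With 50 subjects, true correlation 0, and within-subject correlation w of 0.3, 0.6 or 0.8 in both measures, the variance inflation is about 1 + (m − 1)w² for m scans. The false-positive rate is about 2[1 − Φ(1.96/√inflation)].

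| Scans | w | Inflation | Formula | Simulated, scans as independent |
|---|---|---|---|---|
| 4 | 0.3 | 1.27 | 8% | 7-8% |
| 4 | 0.6 | 2.08 | 17% | 15-16% |
| 4 | 0.8 | 2.92 | 25% | 23-24% |
| 8 | 0.3 | 1.63 | 12-13% | 9-12% |
| 8 | 0.6 | 3.52 | 30% | 27% |
| 8 | 0.8 | 5.48 | 40% | 37-38% |

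The simulated rates are slightly lower, as expected, because grading coarsens the data. A percentile bootstrap resampling whole subjects gave 5-7% in the same settings.

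**Pooling controls.** Take 100 active eyes and controls assumed to have grade 0 and Poisson(1) OCT counts. A Spearman correlation of 0.00 in active eyes becomes 0.61 with 50 controls and 0.71 with 100; a value of 0.44 becomes 0.76 and 0.79.

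**The case against.** The strongest objection is that the T-test is tied to comparing the methods, not to correlating them. Correlation is promised in the Purpose and Introduction, and the open reference to other tools could cover it. This stands. A reader might infer that the plan will use a T-test in place of a correlation, or that correlation has been left out. The documents support neither. They show that the only named method does not serve the aim and that nothing specified does.

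A reader might also infer that a count-against-count test is impossible because the extracted-data list has no cell count. That does not follow. The list does not mention the grade either, yet the analysis paragraph relies on it, so the list may not be exhaustive. Its wording in fact makes count against count a more natural reading than count against grade.

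The power loss in reading (c) is modest and depends on the cut and on N. With the cut at 1+ and above, N = 100 and ρ = 0.3, power was 65% against 76% for Spearman in a separate run. At N = 300 both exceed 97%. The case against reading (c) is that it measures strength indirectly, not that it lacks power.

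Finally, feasibility is the first listed purpose, the algorithm is still to be developed, and care is not altered. That limits the weight of the point. It does not remove it, since the protocol also intends to judge whether the correlation could guide treatment.

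**Conclusion.** The point holds as a recommended change to the analysis, not as proof that a wrong analysis will be run. That the named test does not measure the stated quantity, and that no estimate, limit or handling of repeat scans is given, rests on the text alone. Taken by itself, the missing limit would be close to a missing detail. Together with a test of means and clustered data, it leaves the correlation aim without a working method.

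The sizes are illustrative. On the assumed data, a paired test rejects about 100% (count against grade) or 4-5% (count against count, equal scale) whatever the correlation from 0 to 0.9, and about 23% rising to 89% if OCT reads 20% low. An independent-scan analysis would give about 7-38% false positives. That range requires that scans be treated as independent, which the plan does not say, and that the assumed within-subject correlations apply.

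**What to change.** Reword the last paragraph of Methods before analysis:

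1. Make the main method comparison a Spearman correlation of OCT count with clinical grade, separately for the manual and automated counts and reported by OCT system.
2. Use all scans, with a 95% confidence interval from a bootstrap that resamples whole subjects, keeping all of a subject's scans (and both eyes, if both are used) together.
3. State in advance the lower confidence limit that counts as strong enough. The documents supply no value, so the investigators must choose and justify it.
4. If controls are pooled, also report the correlation in eyes with grade 0.5+ or higher alone.
5. Keep the T-test as a secondary description of mean bias or of group differences, and say which.
6. Apply the same subject-level clustering to the correlation with treatment and outcomes.
7. Add the clinical grade explicitly to the extracted data, where only inflammation status is now listed.

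The cost is wording and slightly more analysis work. Intervals will be wider than those from an independent-scan analysis. The percentile bootstrap may still be slightly narrow: it missed the true value in 5-7% of 1,000 runs with 50 or 100 subjects. The active-eye correlation may look less favourable than a pooled one.

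### Purposes 2 to 4 set anterior chamber cell density as the OCT measure, but the hypothesis and both analyses use a cell count with no denominator, and the t-test against the clinical method has no common unit.

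*Combined protocol and SAP*

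**What the plan says.** The Purpose section is mixed. Its first item concerns feasibility and names a count: "To determine the feasibility of objective measurement of anterior chamber (AC) cell count utilizing" the two OCT systems. The other three name density. The algorithms are to process the "images and objectively measure the cell density". The third item is "To correlate the objective AC cell density measurement and the subjective clinical AC cell grading". The fourth is "To compare the objective AC cell density measurement with subject treatment outcomes".

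After that the measure is a count. The study plan at the end of the Introduction is to "automate the objective reading of AC cell count from these images, correlate the objective count with the subjective clinical grade". The Hypothesis concerns "Automated, objective measurement of anterior chamber cell count". In the last paragraph of Methods, specialists and then an algorithm mark white cells on each image. The resulting counts are set against the clinical grade and then against treatment plans and outcomes. A t-test, with further tools left open, "will be used to compare the study and the clinical AC cell count methodologies".

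The clinical reference is described in the Introduction. Clinicians "manually count the number of leukocytes in a 1mm by 1mm beam of light in the AC visible through a slit lamp stereoscope", and the result is reported as one of six ordered grades with unequal bands.

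Methods also says that either OCT system, or both, may be used, and that the choice depends on availability. A subject stays on the system used at the first visit. Some subjects are asked to use both so that the results can be compared.

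**The concern.** Purposes 3 and 4 correspond one to one with the two planned analyses, and in both pairs the measure changes from density to count. A count of cells on an image depends on two things: how many cells there are per unit of chamber, and how much chamber is in the image. Only the first is inflammation. If the two systems capture different fields, pooled results carry that difference as if it were signal or noise in the eye. The planned check on subjects scanned with both systems could not then separate device disagreement from a difference in field.

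The t-test raises a second problem. It is offered for comparing the OCT method with the clinical one, but the two results are on different scales. The stated aim is correlation, which a test of means does not address.

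**Working it through.** **Step 1. Where the OCT measure is named.**

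| Place | Measure |
|---|---|
| Purpose 1 (feasibility) | count |
| Purpose 2 (algorithm) | density |
| Purpose 3 (against clinical grade) | density |
| Purpose 4 (against outcomes) | density |
| End of Introduction | count |
| Hypothesis | count |
| Methods, last paragraph, against clinical grade | count |
| Methods, last paragraph, against treatment and outcomes | count |

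Row 3 should match row 7, and row 4 should match row 8. Neither does.

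**Step 2. Could an analyst recover density from the plan?** No. The protocol gives no unit, area or volume, number of scan lines, region of interest, scan pattern or conversion.

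**Step 3. How a count behaves.** Expected count = density × field scanned. If the field is constant, count is density times a constant, and every correlation is unchanged. If the field differs by a ratio R at the same density, the count differs by R.

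The Introduction's own example gives a yardstick. A rise from 28 to 48 cells is (48 − 28)/28 = 71%, as stated there. A field 48/28 = 1.71 times as large would produce the same rise at unchanged density.

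**Step 4. Effect on correlation, under assumptions.** Let log density have SD s and log field have SD t, independent of each other, and ignore counting noise. Then corr(log count, log density) = s / √(s² + t²). The protocol supplies neither s nor t, so both are assumed:

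| s | t = 0.1 | t = 0.25 | t = 0.5 |
|---|---|---|---|
| 0.5 | 0.981 | 0.894 | 0.707 |
| 1.0 | 0.995 | 0.970 | 0.894 |
| 1.5 | 0.998 | 0.986 | 0.949 |

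For two systems, each with a fixed field, differing by a ratio R, with a share p of scans on one of them, t² = p(1 − p)(ln R)². With R = 2 and p = 0.5, t² = 0.25 × 0.6931² = 0.120.

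- s = 1.0: 1/√1.120 = 0.94.
- s = 0.5: 0.5/√0.370 = 0.82.

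An even split is the worst case for a given R. The protocol generally prefers one system, so the split may be uneven and the loss smaller. Within either system t = 0 in this example, so a correlation computed by system loses nothing.

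**Step 5. The t-test.** One side is a count from an OCT field of unstated size. The other is a grade with bands of unequal width, based on a 1 mm by 1 mm beam. Their mean difference has no unit. Dividing the OCT count by its area does not cure this, because the clinical side is still a grade. A rank correlation needs only the ordering on each side.

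**The case against.** The strongest reply is that the protocol uses the two words loosely. Purpose 3 and the end of the Introduction describe the same aim, one with density and the other with count, and Methods even calls the clinical grading a count. Purpose 2 says the algorithm yields density, so the algorithm's output in Methods may be density under another name. This is possible, and it means that a reader should not infer that an unnormalised count is certainly what will be analysed. It does not close the gap, because no denominator is given under either reading.

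A reader might also infer that OCT counts cannot be compared across eyes and visits. The documents do not show that. Each subject keeps one system, follow-up scans repeat the same procedure, and no passage says that the field varies. What stands is that no fixed scan pattern is written down. Between systems the doubt is stronger. The protocol plans a check there but defines no analysis for it.

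On the t-test, the sentence does not spell out a mean difference between OCT and slit-lamp counts, and a t-test could serve to compare OCT results between groups. That is fair. But the sentence names the two methods as the things compared, and for that purpose the test does not fit. To say that it would mainly test field size is speculation. Correlation with grade is already among the aims, so the fix brings the analysis paragraph into line with them.

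**Conclusion.** The point holds in a limited form. The OCT measure changes from density in purposes 2 to 4 to count in the hypothesis and both analyses. No denominator is stated, and the t-test does not suit a comparison with an ordinal clinical grade.

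The size of the effect is unknown, because the protocol gives no scan geometry. It ranges from nothing, if the field is constant, to a correlation between log count and log density of 0.94 or 0.82 for a twofold, evenly split difference between systems. The widest combination tabulated gives 0.707. These figures rest on assumed spreads and on independence of field and density. They do not show that the correlation with grade will be weak.

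The change should be made before the images are analysed. It also removes a later choice between count and density made with the results in view.

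**What to change.** - In the Hypothesis and the last paragraph of Methods, name one OCT measure: anterior chamber cell density, defined as cells identified divided by the anterior chamber area in the analysed scans. Use it for both manual and automated readings, with the same denominator for both systems. Bring the count wording in Purpose 1 and the Introduction into line.
- State one fixed scan pattern per system.
- Replace the t-test between OCT and clinical counts with rank correlation of OCT density against clinical grade, shown by system. Use the grade, because the plan does not say that a numerical slit-lamp count will be recorded.

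The cost is a wording change plus some extra image processing to outline the chamber area on the analysed scans. No additional subjects or visits are needed.
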